9.5. Electrocardiograms

Electrocardiogram (ECG) parameters will include heart rate, PR, RR, QRS, QT, and QTcF intervals.

Triplicate 12-lead ECGs will be obtained at below timepoint and at screening:

First participant within each cohort	Subsequent participants within each cohor	
Day 1 (pre-dose, 2h, 6h, and 12h post IV	Day 1 (pre-dose, 2h, 6h, and 12h post IV	
dose)	dose)	
Day 2 (24 hours post IV dose)	Day 2 (24 hours post IV dose)	

First participant within each cohort	Subsequent participants within each cohort
Day 3 (48 hours post IV dose)	Day 3 (48 hours post IV dose)
Day 5 (96 hours post IV dose)	Day 5 (96 hours post IV dose)
Day 8 (1 week post IV dose)	
Day 15 (pre-dose, 2h, 6h, and 12h post SC	Day 8 (pre-dose, 2h, 6h, and 12h post SC dose
dose 1)	1)
Day 16 (24 hours post SC dose 1)	Day 9 (24 hours post SC dose 1)
Day 17 (48 hours post SC dose 1)	Day 10 (48 hours post SC dose 1)
Day 19 (96 hours post SC dose 1)	Day 12 (96 hours post SC dose 1)
Day 22 (pre-dose, 2h, 6h, and 12h post SC	Day 15 (pre-dose, 2h, 6h, and 12h post SC
dose 2)	dose 2)
Day 23 (24 hours post SC dose 2)	Day 16 (24 hours post SC dose 2)
Day 29 (pre-dose, 2h, 6h, and 12h post SC	Day 22 (pre-dose, 2h, 6h, and 12h post SC
dose 3)	dose 3)
Day 30 (24 hours post SC dose 3)	Day 23 (24 hours post SC dose 3)
Day 31 (48 hours post SC dose 3),	Day 24 (48 hours post SC dose 3)
Day 36 (1 week post SC dose 3)	Day 29 (1 week post SC dose 3)
Day 65/End of Treatment (EoT) (6 weeks	Day 57 EoT (5 weeks post SC dose 3)
post SC dose 3)	

Note: Predose triplicate 12-lead ECGs will be performed 3 times at approximately 2, 1, and 0.5 hours before the start of dosing.

The average of the triplicate ECG readings at the time points collected will be calculated and used in the summary statistics. The baseline will be defined as the average of the last non-missing assessment (including repeated and unscheduled assessments) before the first dose of study drug administration.

Relative time to dose will be presented for the summary statistics includes:

- Baseline, 2 hours post IV dose, 6 hours post IV dose, 12 hours post IV dose, 24 hours post IV dose, 48 hours post IV dose, 96 hours post IV dose, and 1 week post IV dose;
- Pre SC dose 1, 2 hours post SC dose 1, 6 hours post SC dose 1, 12 hours post SC dose 1, 24 hours post SC dose 1, 48 hours post SC dose 1, and 96 hours post SC dose 1;
- Pre SC dose 2, 2 hours post SC dose 2, 6 hours post SC dose 2, 12 hours post SC dose 2, 24 hours post SC dose 2;
- Pre SC dose 3, 2 hours post SC dose 3, 6 hours post SC dose 3, 12 hours post SC dose 3, 24 hours post SC dose 3, 48 hours post SC dose 3, 1 week post SC dose 3, and 8 weeks post SC dose 3.

Summary statistics and changes from baseline of calculated average for heart rate, PR, RR, QRS, QT, and QT interval corrected for heart rate using Fridericia's formula (QTcF) will be presented by relative time to dose and by each dose.

An outlier analysis will be performed. Summary table showing the frequency and percentage of participants who meet any of the following criteria at each relative time to dose will be produced.

• QT, QTcF interval:

- \circ $\leq 450 \text{ msec}$
- \circ > 450 and \leq 480 msec
- \circ > 480 and \leq 500 msec
- \circ > 500 msec
- QT, QTcF interval increases from baseline:
 - $\circ \le 30 \text{ msec}$
 - \circ > 30 and \leq 60 msec
 - \circ > 60 msec

All ECG findings will be presented in a data listing.

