Hypersensitivity reaction labs (tryptase, IgE, C5b-9, chemistry, hematology, and urinalysis)	Х					$\leftarrow X^i\!\!\rightarrow$					
Concomitant medications			←Monitor	continual	ly after ICF is	signed→					
Adverse events review/evaluation	$\leftarrow Monitor continually after ICF is signed \rightarrow$										

Note: When scheduled at the same timepoint, the triplicate ECG should be performed first, followed by vital signs assessments, and then PK/PD sampling.

^a All postdose timepoints are relative to the start of the IV infusion/time of the SC injection (ie, time 0 hr) except the ECG, PK/PD sample, and infusion site evaluation performed/collected at the EoI (see footnote d).

^b Only if the Investigator approves the day prior as an Outpatient Visit.

^c Each 12-lead ECG will be performed in triplicate (sequentially within a 15-minute period) and should not be assessed after any major meal (ie, major meals should be withheld until after ECG assessments). At least the last of the 3 predose triplicate 12-lead ECG will be performed within half an hour prior to dosing. The ECGs at 2, 6, and 12 hours postdose have a window of \pm 30 minutes.

^d ECG and PK/PD (in that order) performed/collected at EoI (t_{max}) each have a window of + 15 minutes.

Protocol Amendment 5 10 Mar 2022

ALXN1850-HPP-101

- ^e Vital signs will be measured every 15 minutes for the first hour after dosing, with a window of \pm 5 minutes. Other vital signs measurements have a window of \pm 15 minutes.
- ^f A window of ± 30 minutes from each postdose time point is permitted for all PK/PD timepoints except EoI. Predose PK/PD windows are -1 hour (SC doses) and -3 hours (IV dose).
- ^g Injection/infusion site evaluations will be performed during the infusion, after I/EoI, and then within 15 minutes (+ 5 minutes) after I/EoI. The rest of the timepoints have a window of \pm 15 minutes.
- ^h Predose and postdose abbreviated PEs are allowed at the predose or dosing day, and on the day after dosing or 2 days after dosing, depending on when the participant is admitted and discharged.
- ⁱ If a hypersensitivity reaction is suspected, samples should be collected as soon as possible (within 1 hour of the reaction) and again at 2 and 8 hours (+ 1 hour window each) after the 1st sample. The Day 1 predose sample will only be analyzed for participants with a reported suspected hypersensitivity reaction at any time following the first dose.

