- Hypersensitivity Reaction Labs

To the sites participating in the above named and numbered clinical study, this letter serves to inform you about the following administrative change to the above referenced protocol version.

• Clarifications in Section 1.3 Schedule of Activities, Table 1, 2 and 3: Postdose timepoints evaluation

This document provides clarification that all postdose timepoints are relative to the START of the IV infusion/injection (time 0) EXCEPT for ECG and PK/PD samples, performed/collected at EoI.

• Clarifications in Section 1.3 Schedule of Activities, Table 1, 2 and 3: Injection/infusion site evaluation

This document provides clarification on the timeframes for injection/infusion site evaluation. Injection/infusion site evaluations have to be performed from Time 0h and every 15 minutes (+ 5 minutes) until the 1st hr after the start of the injection/infusion. The rest of the timepoints have a window of \pm 15minutes.

• Clarifications in Section 1.3 Schedule of Activities, Table 1, 2 and 3: Hypersensitivity Reaction Labs

The Hypersensitivity Reaction labs have been clarified to reconcile the information from Table 1 and Table 2 with Table 3.

- If a hypersensitivity reaction is suspected, in general study overview for 1st and subsequent participants (table 1 and 2): hypersensitivity reaction labs (tryptase, IgE, C5b-9) as well as chemistry, hematology, and urinalysis samples should be collected as soon as possible (within 1 hour of the reaction) and again at 2 and 8 hours (+ 1 hour window each) after the 1st sample. The Day 1 predose samples will only be analyzed for participants with a reported suspected hypersensitivity reaction at any time following the first dose. If the participant is not in the clinic, these samples do not need to be collected and suspected hypersensitivity reaction persists beyond 8 hours, the CRU should contact the MM for guidance.
- If a hypersensitivity reaction is suspected, the day of the dosing (table 3): hypersensitivity reaction labs (tryptase, IgE, C5b-9) as well as chemistry, hematology, and urinalysis samples should be collected as soon as possible (within 1 hour of the reaction) and again at 2 and 8 hours (+ 1 hour window each) after the 1st sample. The Day 1 predose samples will only be analyzed for participants with a reported suspected hypersensitivity reaction at any time following the first dose.

Page 1 of 5 Alexion Confidential

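### SAP 9.5's ECG time-point list leaves out the end-of-infusion and end-of-treatment ECGs and names an 8-week point at which no ECG is scheduled

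*SAP*

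**What the plan says.** **Protocol.** Section 1.3, Table 3 marks a triplicate ECG at end of infusion (EoI) for the IV dose. Its footnote d reads "ECG and PK/PD (in that order) performed/collected at EoI" and labels that moment tmax, with a window of +15 minutes. Administrative Change Letter #6, filed with the protocol, confirms that this ECG exists: post-dose times count from the start of dosing "EXCEPT for ECG and PK/PD samples, performed/collected at EoI". Tables 1 and 2 place the last ECG at the end-of-treatment (EoT) visit, Day 65 or Day 57, and leave the end-of-study (EoS) column, Day 85 or Day 78, blank. Section 9.4.2 asks for averages and changes from baseline at the times collected, and for outlier counts at each visit.

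**SAP 9.5, collection schedule.** The first day is given as "Day 1 (pre-dose, 2h, 6h, and 12h post IV" dose, with no EoI. The last ECG for subsequent participants is "Day 57 EoT (5 weeks post SC dose 3"). For first participants it is Day 65, labelled 6 weeks.

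**SAP 9.5, times for the tables.** The list opens "Baseline, 2 hours post IV dose, 6 hours post IV dose, 12 hours post IV dose, 24 hours post IV dose" and, for the third SC dose, closes "48 hours post SC dose 3, 1 week post SC dose 3, and 8 weeks post SC dose 3". The outlier table is to be produced at each of these relative times. All ECG findings are also listed.

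**The concern.** The relative-time list decides which ECGs reach a table, and it does not match the ECGs the protocol schedules. Two collected time points have no row, and one row has no scheduled ECG behind it. The SAP is therefore narrower than Protocol 9.4.2 without saying so. No reason is given for leaving out EoI, and the SAP includes EoI in its collection schedules for PK (8.2), infusion-site evaluation (9.8) and PD (Section 10), so an oversight is more likely than a decision.

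At stake is the completeness of the descriptive ECG summaries in a first-in-human study. The IV ECG closest in time to the end of dosing, and the last ECG on study, would both be missing from the change-from-baseline and outlier tables.

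**Working it through.** **1. Match the schedules.**

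| Time point | Protocol Tables 1–3 | SAP 9.5 schedule | SAP 9.5 relative-time list |
|---|---|---|---|
| EoI, IV dose | ECG | absent | absent |
| EoT, Day 65/57 | ECG | present | absent |
| 8 weeks after SC dose 3, Day 85/78 | no ECG | absent | present |

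The other post-baseline time points agree.

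**2. Can the 8-week row be a loose label for EoT?** SC dose 3 is on Day 29 (first participants) or Day 22 (subsequent). The visit windows in Tables 1 and 2 are −3/+7 days for EoT and −7/+14 days for EoS. Weeks after SC dose 3 = (visit day − dose day) / 7.

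- EoT, first: 65 − 29 = 36 days = 5.1 weeks; window 33 to 43 days = 4.7 to 6.1 weeks.
- EoT, subsequent: 57 − 22 = 35 days = 5.0 weeks; window 32 to 42 days = 4.6 to 6.0 weeks.
- EoS, first: 85 − 29 = 56 days = 8.0 weeks. EoS, subsequent: 78 − 22 = 56 days = 8.0 weeks. Window for both: 49 to 70 days = 7.0 to 10.0 weeks.

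The windows do not overlap, so an in-window EoT ECG cannot fall at 8 weeks. SAP 8.2 and 9.3 also use the 8-week label for Day 85/78. An unplanned ECG at EoS would not fill the row either, because SAP Section 4 keeps unscheduled results out of summary tables except for determining baseline.

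**3. Count the post-baseline ECG time points.**

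- Day 1 after dosing: EoI, 2, 6 and 12 hours = 4.
- Three SC dosing days, each pre-dose, 2, 6 and 12 hours: 3 × 4 = 12.
- Other days, first participants (2, 3, 5, 8, 16, 17, 19, 23, 30, 31, 36, 65) = 12. Total 4 + 12 + 12 = 28.
- Other days, subsequent participants (2, 3, 5, 9, 10, 12, 16, 23, 24, 29, 57) = 11. Total 4 + 12 + 11 = 27.

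Omitted share: 2/28 = 7.1% and 2/27 = 7.4%.

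**4. Triplicates affected.** If 15 participants are dosed and all reach EoT, 15 + 15 = 30. If only the planned minimum of 9 reach EoT, 15 + 9 = 24.

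**5. The Day 65 label.** SAP 9.5 calls Day 65 6 weeks and Day 57 5 weeks after SC dose 3. They are 36 and 35 days. SAP 8.2 calls both 5 weeks.

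**The case against.** **A safety signal could be hidden.** A reader might infer this, and the documents do not support it. Protocol 8.2.3.1 has the investigator review every recorded ECG and follow clinically significant abnormalities to resolution. Under Protocol 10.3.1, ECG findings judged clinically significant are adverse events, so they enter the tables of treatment-emergent events, which are the primary endpoint. Protocol 6.6.1 includes ECG findings in the Safety Review Committee's data for escalation to Cohort 2. What remains is an exceedance not judged clinically significant. That would be confined to a listing, which can be read in full with about 15 participants.

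**The plan misses the peak-exposure ECG.** A reader might also infer this from the tmax label. It is not shown. Protocol Table 5 predicts, for 15 mg IV, Cmax 4.3 µg/mL and AUC over 0–168 hours of 325 µg·h/mL. Assuming mono-exponential decline after a short infusion, 4.3 × (1 − e^(−168k)) / k = 325 gives k ≈ 0.011 per hour and a half-life of about 62 hours. The concentration 2 hours after the peak is then e^(−2k) ≈ 98% of Cmax, so the 2-hour ECG, which is in the tables, may already be near peak. A rapid distribution phase would lower that figure, and the infusion rate is left to the Pharmacy Manual. Protocol 2.2.2.3 also reports no drug-related change in qualitative electrocardiography in monkeys.

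**Other wording already covers it.** SAP 9.5 says the triplicate average at the times collected goes into the summaries, and its schedule includes EoT. The EoT gap is therefore a conflict within the section rather than a decision to exclude data. This does not help EoI, which is absent from the SAP's ECG schedule as well, and it still leaves the programmer to choose between two parts of one section.

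**Conclusion.** The mismatch is real and needs correcting. The relative-time list omits EoI and EoT and includes a point with no scheduled ECG. About 7% of scheduled post-baseline ECG time points per participant (2 of 27 or 28; 24 to 30 triplicates on the assumptions shown) would be missing from the change-from-baseline and outlier tables, and one row would be empty or, if EoT data were placed there, mislabelled. This assumes that the list is programmed as written.

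The consequence is limited to the completeness of descriptive tables. No data are lost, clinically significant findings still reach the adverse-event analysis, and the primary endpoint (incidence of treatment-emergent adverse events and serious adverse events) is unaffected. The documents do not establish that the EoI ECG is the one most likely to show a QTcF effect. They do show that the protocol schedules it and labels it tmax, which is reason enough for a row.

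**What to change.** In SAP 9.5:

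- Add end of infusion (IV dose) to the ECG collection schedule and to the relative-time list.
- Replace the 8-week entry in the relative-time list with EoT (Day 57/65, 5 weeks after SC dose 3).
- Change the 6-week label on Day 65 to 5 weeks, so that first and subsequent participants fall in the same row. SAP 9.2 carries the same label.

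A row in the outlier table for any post-baseline exceedance would be a useful option, but neither document calls for it and the mismatch does not require it.

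The cost is SAP wording and two table rows, one added and one replaced. No protocol change or extra data collection is needed.

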9.6. Ophthalmological Examination

Ophthalmological examinations will be performed at the Screening and EoT.

Ophthalmological examinations results will be presented in a data listing.

9.7. Renal Ultrasound

A renal ultrasound will be performed at the Screening and EoT.

Renal ultrasound results will be presented in a data listing.

9.8. Injection or Infusion Site Evaluation

Subcutaneous injection- or IV infusion-site evaluations will be performed at below timepoint:

First participant within each cohort	Subsequent participants within each cohort
Day 1 (0h and EoI, every 15 minutes for	Day 1 (0h and EoI, every 15 minutes for first hour,
first hour, 2h, 6h, and 12h post IV dose)	2h, 6h, and 12h post IV dose)
Day 2 (24 hours post IV dose)	Day 2 (24 hours post IV dose)
Day 3 (48 hours post IV dose)	Day 3 (48 hours post IV dose)
Day 8 (1 week post IV dose)	
Day 15 (0h and EoI, every 15 minutes for	Day 8 (0h and EoI, every 15 minutes for first hour,
first hour, 2h, 6h, and 12h post SC dose	2h, 6h, and 12h post SC dose 1)
1)	
Day 16 (24 hours post SC dose 1)	Day 9 (24 hours post SC dose 1)
Day 17 (48 hours post SC dose 1)	Day 10 (48 hours post SC dose 1)
Day 22 (0h and EoI, every 15 minutes for	Day 15 (0h and EoI, every 15 minutes for first
first hour, 2h, 6h, and 12h post SC dose	hour, 2h, 6h, and 12h post SC dose 2)
2)	
Day 23 (24 hours post SC dose 2)	Day 16 (24 hours post SC dose 2)
Day 29 (0h and EoI, every 15 minutes for	Day 22 (0h and EoI, every 15 minutes for first
first hour, 2h, 6h, and 12h post SC dose	hour, 2h, 6h, and 12h post SC dose 3)
3)	
Day 30 (24 hours post SC dose 3	Day 23 (24 hours post SC dose 3)
Day 31 (48 hours post SC dose 3)	Day 24 (48 hours post SC dose 3)
Day 36 (1 week post SC dose 3)	Day 29 (1 week post SC dose 3)

Hypersensitivity reaction labs (tryptase, IgE, C5b-9, chemistry, hematology, and urinalysis) will be performed at below timepoint:

First participant within each cohort	Subsequent participants within each cohort	
Day 1 (predose)	Day 1 (predose)	
During and postdose: within 1 hour of a	During and postdose: within 1 hour of a	
hypersensitivity reaction. 2 hour and 8	hypersensitivity reaction. 2 hour and 8 hour after	
after first sample	first sample	

Samples will only be analyzed for participants who experience systemic acute hypersensitivity reactions to study drug and assessed in select participants at the Sponsor's discretion.

Relative time to dose will be presented for summary statistics which includes:

For injection or infusion site evaluation:

- Oh and EoI, every 15 minutes for first hour, 2h, 6h, and 12h post IV dose, 24 hours post IV dose, 48 hours post IV dose, and 1 week post IV dose;
- 0h and EoI, every 15 minutes for first hour, 2h, 6h, and 12h post SC dose 1, 24 hours post SC dose 1, and 48 hours post SC dose 1;
- 0h and EoI, every 15 minutes for first hour, 2h, 6h, and 12h post SC dose 2, 24 hours post SC dose 2;
- Oh and EoI, every 15 minutes for first hour, 2h, 6h, and 12h post SC dose 3, 24 hours post SC dose 3, 48 hours post SC dose 3, and 1 week post SC dose 3.

For hypersensitivity reaction labs:

- Predose Day 1;
- During and postdose: As soon as possible (within 1 hour of reaction), and again at 2 and 8 hours after the first sample;
- As soon as possible (within 1 hour of reaction), and again at 2 and 8 hours after the first sample;

Summary statistics and change from baseline for SC injection- or IV infusion-site evaluations and hypersensitivity reaction will be presented by relative time to dose.

The results for SC injection- or IV infusion-site evaluations and hypersensitivity reaction will be presented in data listings.

9.9. Other Safety Data

The following other safety assessments will be performed:

- Other safety laboratory tests: intact 25-hydroxy (25-OH) Vitamin D; the following tests are to be conducted in case of an acute injection-associated reaction: tryptase (Alexion), terminal complement complex C5b-9 (Alexion), IgE (Alexion), hematology, chemistry, and urinalysis panels
- Urine electrolyte: urine for calcium, urine for phosphorus, and urine for creatinine
- Follicle stimulating hormone (FSH): confirmation of post-menopausal state

- Human immunodeficiency virus (HIV)-1 and HIV-2 antibodies, hepatitis B surface antigen (HbsAg), anti-hepatitis B core antigen immunoglobulin G (IgG) + immunoglobulin M (if IgG positive) and hepatitis C virus antibodies (anti-hepatitis C virus)
- Serum or urine human chorionic gonadotropin (bHCG) pregnancy test: as needed for women of childbearing potential
- Cross-reactive immunological material assay

Urine for calcium, phosphorus, and creatinine as well as optional phosphoethanolamine (PEA), samples will be collected on Day -1, Day 2, Day 3, Day 8, Day 16, Day 17, Day 23, Day 30, Day 31, and Day 36 for first participant within each cohort, and on Day -1, Day 2, Day 3, Day 9, Day 10, Day 16, Day 23, Day 24, and Day 29 for subsequent participants within each cohort. Optional PEA samples will additionally be collected at screening and Day 65 for first participants and at screening and day 57 for subsequent participants.

Pregnancy test will be performed at screening, Day -1, Day 14, Day 21, and Day 28 for first participant within each cohort, and at screening, Day -1, Day 7, Day 14, Day 21, Day 29, Day 43, Day 57, and Day 78/ED/EoS for subsequent participants within each cohort. A highly sensitive serum bHCG will be performed at Screening and on Day -1; urine tests will be performed during subsequent visits.

Hepatitis B and C, HIV, FSH, and 25-OH vitamin D will be performed at Screening.

Cross-reactive immunological material assay will be performed on Day 1.

Other laboratory tests (including hepatitis B and C, HIV, FSH, and 25-OH vitamin D, urine for calcium, phosphorus, PEA, and creatinine, and pregnancy) will be presented in a separate data listing.

Cross-reactive immunological material assay will be listed in a data listing.

10. Pharmacodynamic Analysis

All PD analyses will be performed on the PD Set and will be summarized by relative time to dose.

Pharmacodynamic analysis (PPi, PLP, and PL) will be performed at below timepoint:

First participant within each cohort	Subsequent participants within each cohort
Day 1 (pre IV dose); EoI (end of infusion)	Day 1 (pre IV dose); EoI (end of infusion)
Day 2 (24 hours post IV dose)	Day 2 (24 hours post IV dose)
Day 3 (48 hours post IV dose)	Day 3 (48 hours post IV dose)
Day 5 (96 hours post IV dose)	Day 5 (96 hours post IV dose)
Day 8 (1 week post IV dose)	
Day 15 (pre SC dose 1)	Day 8 (pre SC dose 1)
Day 16 (24 hours post SC dose 1)	Day 9 (24 hours post SC dose 1)
Day 17 (48 hours post SC dose 1)	Day 10 (48 hours post SC dose 1)
Day 19 (96 hours post SC dose 1)	Day 12 (96 hours post SC dose 1)
Day 22 (pre SC dose 2)	Day 15 (pre SC dose 2)
Day 23 (24 hours post SC dose 2)	Day 16 (24 hours post SC dose 2)
Day 29 (pre SC dose 3)	Day 22 (pre SC dose 3)

Page 24 of 29

First participant within each cohort	Subsequent participants within each cohort
Day 30 (24 hours post SC dose 3)	Day 23 (24 hours post SC dose 3)
Day 31 (48 hours post SC dose 3),	Day 24 (48 hours post SC dose 3)
Day 36 (1 week post SC dose 3)	Day 29 (1 week post SC dose 3)
Day 51 (3 weeks post SC dose 3)	Day 43 (3 weeks post SC dose 3)
Day 65 (5 weeks post SC dose 3)	Day 57 (5 weeks post SC dose 3)
Day 85/ED/EoS (8 weeks post SC dose 3)	Day 78/ED/EoS (8 weeks post SC dose 3)

Relative time to dose includes:

- Baseline, 24 hours post IV dose, 48 hours post IV dose, 96 hours post IV dose, and 1 week post IV dose;
- Pre SC dose 1, 24 hours post SC dose 1, 48 hours post SC dose 1, and 96 hours post SC dose 1;
- Pre SC dose 2, 24 hours post SC dose 2;
- Pre SC dose 3, 24 hours post SC dose 3, 48 hours post SC dose 3, 1 week post SC dose 3, 3 weeks post SC dose 3, 5 weeks post SC dose 3, and 8 weeks post SC dose 3.

Summary statistics will be presented for absolute, change from baseline, and percent change from baseline for PLP, PLP/PL ratio, and PPi by cohort and relative time to dose for all participants, and will be further repeated by each ADA status (ADA negative and ADA positive, and/or pre-existing immunogenicity, treatment-emergent ADA responses, and treatment-boosted ADA responses if data permits). This summary table will be repeated including all participants up to 1 week post IV dose and subsequent participants for the remaining relative time to dose.

Absolute, change, and percent change from the baseline in mean plasma PLP, PLP/PL ratio, and PPi concentration versus time data will be presented graphically by cohort and by ADA status (ADA negative and ADA positive, and/or pre-existing immunogenicity, treatment-emergent ADA responses, and treatment-boosted ADA responses if data permits) over timepoints relative to dose for all participants. This mean figure will be repeated including all participants up to 1 week post IV dose and subsequent participants for the remaining relative time to dose. In addition, the value of plasma PLP, PLP/PL ratio, and PPi for each participant will be presented graphically overlaid with ADA status over timepoints relative to dose.

All data for PPi, PLP, and PL will be presented in data listings.

11. Immunogenicity Analysis

All immunogenicity analyses will be performed on the Immunogenicity Analysis Set.

Asfotase alfa ADA and NAb will only be tested in participants who have previously received asfotase alfa. Immunogenicity analyses (ALXN1850 ADA and NAb) will be performed on samples collected at timepoint shown below:

First participant within each cohort	Subsequent participants within each cohort
Day 1 (pre IV dose)	Day 1 (pre IV dose)
Day 8 (1 week post IV dose)	
Day 15 (pre SC dose 1)	Day 8 (pre SC dose 1)
Day 22 (pre SC dose 2)	Day 15 (pre SC dose 2)
Day 29 (pre SC dose 3)	Day 22 (pre SC dose 3)

Page 25 of 29

First participant within each cohort	Subsequent participants within each cohort
Day 36 (1 week post SC dose 3)	Day 29 (1 week post SC dose 3)
Day 51 (3 weeks post SC dose 3)	Day 43 (3 weeks post SC dose 3)
Day 65 (5 weeks post SC dose 3)	Day 57 (5 weeks post SC dose 3)
Day 85/ED/EoS (8 weeks post SC dose 3)	Day 78/ED/EoS (8 weeks post SC dose 3)

Immunogenicity testing (asfotase alfa ADA and NAb) will be performed at Screening for participants who have previously received asfotase alfa.

Anti-drug antibody variables include ADA response category incidence and titer over the duration of the study will be defined as:

- ADA negative: ADA negative response in the ADA assay at all time points.
- ADA positive: include participant with a positive response in the ADA assay at any time point will be categorized as follows:
 - O Pre-existing immunogenicity: Defined as ADA positive result in the assay at baseline with all post first dose ADA results negative or a positive result at baseline with all post first dose ADA results less than 4 folds over the baseline titer levels.
 - Treatment-emergent ADA responses: Defined as a positive result in the ADA assay post first dose, when baseline results are negative or missing.
 - Treatment-boosted ADA responses: Defined as a positive result in the ADA assay post first dose, that is greater than or equal to 4-fold over baseline titer levels, when baseline results are positive.

NAb response category will be defined as below

- NAb positives: a positive result in the NAb assay post first dose, in a participant with treatment-emergent or treatment-boosted ADA responses.
- Or will be NAb negative.

The incidence of ADA response categories (negative, pre-existing immunogenicity, treatment-emergent ADA responses, and treatment-boosted ADA response) will be summarized as absolute occurrence (n) and percentage (%) by cohort. The summary statistics of maximum ADA titer levels will be summarized for ADA positive participants by cohort. Listing of maximum ADA titer level for ADA positive participants will be provided.

NAb positive and NAb negative will be summarized as absolute occurrence (n) and percentage (%) by cohort. Listing for NAb positive participants will be provided for treatment-emergent and treatment boosted participants.

The ADA titer will be summarized by cohort and relative to each dose. The mean and individual ADA titer will be presented graphically by cohort over time.

Relative time to dose includes: baseline; 1 week post IV dose, pre SC dose 1; pre SC dose 2; pre SC dose 3, 1 week post SC dose 3, 3 week post SC dose 3, 5 week post SC dose 3, and 8 week post SC dose 3.

All immunogenicity results will be presented in a data listing.

12. Exploratory Analysis

Blood for PTH will be performed at Screening, and on Day 36 (1 week post SC dose 3) for first participant within each cohort, and on Day 29 (1 week post SC dose 3) for subsequent participants within each cohort.

Bone biomarkers (sCTX, P1NP, osteocalcin) will be performed at below timepoint:

First participant within each cohort	Subsequent participants within each cohort
Day 1 (pre IV dose)	Day 1 (pre IV dose)
Day 36 (1 week post SC dose 3)	Day 29 (1 week post SC dose 3)
Day 65 (5 weeks post SC dose 3)	Day 57 (5 weeks post SC dose 3)
Day 85/ED/EoS (8 weeks post SC dose 3)	Day 78/ED/EoS (8 weeks post SC dose 3)

Pyridoxic acid will be performed at below timepoint:

First participant within each cohort	Subsequent participants within each cohort
Day 1 (pre IV dose)	Day 1 (pre IV dose)
Day 2 (24 hours post IV dose)	Day 2 (24 hours post IV dose)
Day 3 (48 hours post IV dose)	Day 3 (48 hours post IV dose)
Day 5 (96 hours post IV dose)	Day 5 (96 hours post IV dose)
Day 8 (1 week post IV dose)	
Day 15 (pre SC dose 1)	Day 8 (pre SC dose 1)
Day 16 (24 hours post SC dose 1)	Day 9 (24 hours post SC dose 1)
Day 17 (48 hours post SC dose 1)	Day 10 (48 hours post SC dose 1)
Day 19 (96 hours post SC dose 1)	Day 12 (96 hours post SC dose 1)
Day 22 (pre SC dose 2)	Day 15 (pre SC dose 2)
Day 23 (24 hours post SC dose 2)	Day 16 (24 hours post SC dose 2)
Day 29 (pre SC dose 3)	Day 22 (pre SC dose 3)
Day 30 (24 hours post SC dose 3)	Day 23 (24 hours post SC dose 3)
Day 31 (48 hours post SC dose 3),	Day 24 (48 hours post SC dose 3)
Day 36 (1 week post SC dose 3)	Day 29 (1 week post SC dose 3)
Day 51 (3 weeks post SC dose 3)	Day 43 (3 weeks post SC dose 3)
Day 65 (5 weeks post SC dose 3)	Day 57 (5 weeks post SC dose 3)
Day 85/ED/EoS (8 weeks post SC dose 3)	Day 78/ED/EoS (8 weeks post SC dose 3)

Relative time to dose for PTH will be presented for summary statistics will include baseline and 1 week post SC dose 3.

Relative time to dose for bone biomarkers will be presented for summary statistics will include: baseline; 1 week post SC dose 3, 5 week post SC dose 3, and 8 week post SC dose 3.

Relative time to dose will be presented for summary statistics for PA will include:

- Baseline, 24 hours post IV dose, 48 hours post IV dose, 96 hours post IV dose, and 1 week post IV dose;
- Pre SC dose 1, 24 hours post SC dose 1, 48 hours post SC dose 1, and 96 hours post SC dose 1;
- Pre SC dose 2, 24 hours post SC dose 2;

• Pre SC dose 3, 24 hours post SC dose 3, 48 hours post SC dose 3, 1 week post SC dose 3, 3 weeks post SC dose 3, 5 weeks post SC dose 3, and 8 weeks post SC dose 3.

Summary statistics will be presented for absolute, change from baseline, and percent change from baseline for PTH, sCTX, P1NP, and osteocalcin will be presented by relative time to dose and by cohort and overall.

Summary statistics will be presented for absolute, change from baseline, and percent change from baseline for PA will be presented by relative time to dose and by each dose.

Absolute, change, and percent change from the baseline in PTH, PA, sCTX, P1NP, and osteocalcin versus time will be presented graphically by cohort over time.

All data for PTH, PA, sCTX, P1NP, and osteocalcin will be presented in data listings.

13. Interim Analysis

No formal interim analyses will be planned in this study. Before dose escalation is allowed, a safety and PK data review for each dose Cohort will be performed. Database snapshot operational plan and dose selection plan will be referenced for creating the data snapshot.

14. Changes in the Planned Analysis

[figure not shown]
Any changes from this SAP will be documented in the CSR for this study.

15. References

Not applicable.

16. Schema

Figure 1: Study Schema

Notes: Further details of SRC meeting requirements and timelines are provided in the SRC charter.

Completion of EoT assessments (Day 65 [1st participant in each cohort]/ Day 57 [subsequent participants in each cohort] Visit) is the end of the Treatment Period, while completion of EoS assessments (Day 85 [first participant in each cohort]/ Day 78 [subsequent participants in each cohort] Visit) is end-of-study. For the timing of each visit during the study, whether it should be an Outpatient or Inpatient Visit (or either at the Investigator's discretion), its permitted time window, and the assessments to be performed, see Table 1, Table 2, and Table 3.

Telemedicine visits may be performed by study site staff for safety reasons/AE FU.

Abbreviations: D = day, ED = early discontinuation; EoS = end-of-study; EoT = end-of-treatment; FU = follow-up; IV = intravenous; PD = pharmacodynamics; PK = pharmacokinetics; qw = weekly; SC = subcutaneous; SRC = Safety Review Committee

Notes: Further details of SRC meeting requirements and timelines are provided in the SRC charter (Protocol Section 9.6).

Statistical Analysis Plan (SAP) Client Approval Form

Client:	Alexion Pharmaceuticals, Inc	
Protocol Number:	ALXN1850-HPP-101	
Document Description:	Statistical Analysis Plan	
SAP Title:	A Phase 1, Open-label, Dose-escalating Study to Evaluate the Safety, Tolerability, Pharmacokinetics, and Pharmacodynamics of ALXN1850 in Adults with Hypophosphatasia	
SAP Version Number:	2.0	
Effective Date:	05/03/2022	
Author(s):		
For PPD:		
Approved by:		
	03-May-2022 11:48:23 ED	
	Date (DD-MMM-YYYY)	
	03-Мау-2022 12:07:33 в	
	Date (DD-MMM-YYYY)	

Document Number: FORM-02894

v8.0 Page 1 of 2 Effective Date: 22 Nov 2021

Printed on: 3 May 2022

